5.3 Withdrawal Criteria

1. Subjects will be allowed to withdraw from the study at any time upon request
2. Subjects' participation will be terminated if any of the inclusion criteria ceases to be valid or if any exclusion criteria will manifest after enrollment
3. Subjects' participation will be terminated if any significant depression is identified on the collected information on depression. Subjects will also be referred to a mental health professional.

Prior to scheduling, subjects will be screened over a phone interview to determine whether they meet the inclusion and exclusion criteria. All research personnel will have received training in the responsible conduct of human research as required by Washington University's Institutional Review Board (IRB).

6. Human Subjects Research

6.1 Protection of Human Subjects

The study will be performed after proper Washington University Institutional Review Board (IRB) approval of the protocol, consent forms, and recruitment materials. This study will include human subjects and thus will be conducted in conformity to the Helsinki declaration. The study will be conducted under the supervision of the [name] who is experienced in the conduct of human studies on SCS. The motion tracking, EMG, and TMS data will be analyzed qualitatively and quantitatively in collaboration with team members with substantial expertise (laboratories of [name] in the Department of Biomedical Engineering and [name] in the Department of Psychiatry), to identify corticospinal responses associated with movement and transcutaneous SCS.

6.2 Recruitment and Informed Consent

Our recruitment procedure for SCI subjects uses word-of mouth, fliers (posters), and phone calls. Healthy subjects that are affiliated with Washington University will be recruited by flyers, and word of mouth. We will stress in recruitment and during the study that participation is completely voluntary and will not affect their benefits or employment status.

Subjects with SCI will be referred by Drs. [name] and [name] (Washington University School of Medicine, Neurosurgery), [name] (Barnes-Jewish Hospital, Physical Medicine and Rehabilitation, Spinal Cord Injury Medicine), [name] (The Rehabilitation Institute of St. Louis), and [name] (Paraquad, Stephen A. Orthwein Center), and identified through the EPIC system if they meet the recruitment criteria. They will be told about the study in person or contacted by phone and read the "Phone Script". We will make it clear that participation does not imply any certainty for favorable outcome or other benefits.

Recruitment from TRISL and Paraquad will be purely in the form of posting recruitment flyers and referrals. No patient database access will be requested or used.

Subjects will be given verbal (initially) and then written descriptions of the study aims, procedures, risks, and benefits, and will be required to give written informed consent. A member of the investigative team provides all study descriptions, informed consent, and answers all questions. Subjects are informed verbally and in writing that participation is voluntary, and they may refuse to participate and may withdraw from the study at any time without penalty.

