3.1 Rationale for this study

This 1-year study will provide the necessary data to prepare a clinical trial investigating whether activity-dependent reorganization of cortico- and reticulospinal circuits are primary contributors towards the long-lasting improvements in function that have been observed in humans. Moreover, we will study whether different types of training used in rehabilitation can be used to enhance the excitability of these neural structures and evaluate their role in the learning of skilled motor tasks²²⁻²⁵. An understanding of how we can accelerate plasticity through residual cortical and reticulospinal connections may enable the development of rehabilitation strategies that take advantage of patient-specific residual functions to further augment recovery.

4. Study Objectives

The goal of this project is to generate evidence-based knowledge of changes in the short-term excitability of corticospinal and reticulospinal neural structures that may mediate immediate improvements in motor function enabled by SCS.

Aim 1. Determine which kinds of SCS-facilitated movements are mediated by the corticospinal tract. I will use TMS to test whether SCS can enhance motor evoked potential (MEP) response time and amplitude as individuals use their legs to perform motor control tasks with different levels of dexterity.

Aim 2. Determine which kinds of SCS-facilitated movements are mediated by the reticulospinal tract. Using the same protocol, I will test whether SCS can enhance StartReact response time and amplitude.

5. Selection of Subjects – Inclusion/Exclusion Criteria

We plan to include in this study a total of 100 unimpaired and 12 SCI human volunteers over the course of one year.

Data collection will be performed at Washington University in St. Louis Danforth and Medical campus. Subjects will be referred by Drs. [name], [name], [name], [name], and [name], who are co-investigators on this project.

Approximately equal numbers of men and women will be recruited from all ethnic and racial groups. The racial composition of the population in St. Louis is approximately 44% Caucasian, 46% Black or African American, 4% Asian, 4% Hispanic, 2% Other. This will be the expected composition of our volunteer pool, of which the minority portion exceeds the national norm.

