5.1 Healthy volunteers

Inclusion criteria

1. Age between 18 and 65 years
2. Healthy people with no major comorbidities of any organ systems

Exclusion criteria

1. Subjects younger than 18 or older than 65 years
2. Subjects not providing consent or not able to consent
3. Subjects with any acute or chronic pain condition
4. Subjects with any acute or chronic disease of a major organ system
5. Use of analgesics earlier than 5 half-lives after the latest intake prior to study period
6. The use of caffeinated products within 3 hours prior to study period
7. History of epilepsy
8. Implanted metal

9. Active medical problems

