6.6 Inclusion of minorities

All of our studies actively encourage the participation of minorities in the research. Our minority recruiting of healthy subjects typically matches the demographic composition of the Washington University community from which subjects will be recruited (78% white, 21% Black, <1 % Hispanic). The racial composition of the population in St. Louis is approximately 44% Caucasian, 46% Black or African American, 4% Asian, 4% Hispanic, 2% Other. This will be the expected composition of our SCI volunteer pool, of which the minority portion exceeds the national norm.

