7.1 Procedure Schedules – Full Protocol

SCI and Controls – Complete protocol

PROCEDURE	7.2 INITIAL EVALUATION			7.3 AIM 1	7.4 AIM 2
	Visit #1 Functional Mapping	Visit #2 Range of Motion	Visit #3 Familiarization	Visit #4 TMS	Visit #5 StartReact
Kinematic recordings					
EMG recordings					
Transcutaneous SCS					
BoMI					
Motor tasks					
TMS					
StartReact					

7.2 Initial evaluation: Determine the effect of SCS on motor responses and range of motion

To determine an initial baseline for each participant, we will evaluate motor responses elicited by transcutaneous SCS in the initial evaluation phase. Participants will visit the lab for 1) a functional mapping where we measure spinal responses elicited by SCS, 2) a range of motion evaluation where we measure the range of motion on different joints with and without SCS, and 3) a familiarization phase where participants learn to control the body-machine interface using their leg movements supported by SCS.

Participants: 100 unimpaired participants and 12 participants with spinal cord injury (spinal cord injury level C4-T9) with motor impairments in the legs (complete ASIA A, or incomplete ASIA B, C, or D) and in the chronic stage of SCI (>6 months postinjury) will participate in this experiment, which will be submitted for review and approval to Washington University School of Medicine Institutional Review Board. Unimpaired participants will be recruited to perform either one of the five potential visits (Visits# 1-5) or all five visits. Approximately 16 unimpaired participants are expected to complete each type of protocol. SCI participants will be recruited for the five visits in total.

Experiments with unimpaired, control participants will be used to refine collection procedures and instruments and to prepare an improved, more refined research design that will ensure effective and high-quality data collection with SCI participants. Data collected on control subjects will also be used to establish baseline behavior for comparison of SCI participant task performance and may be used to generate generalizable knowledge.

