Transcranial magnetic stimulation (TMS): Motor evoked potentials (MEPs) in the tibialis anterior and rectus femoris muscles will be evoked by TMS of the contralateral motor cortical leg area using a Magstim 200² stimulator (Magstim, UK) through a double cone coil and a monophasic current waveform delivered at 4-s intervals. The motor threshold for both muscles will be identified⁶⁵ and that intensity will be used to elicit and average twenty MEPs at each timepoint²⁴. Average MEP response amplitude will be used to quantify changes in corticospinal tract excitability¹⁵. If no motor threshold is detected at 100% device stimulation intensity due to SCI (and interrupted circuits), the 100% stimulation intensity or the maximum tolerable intensity will be used. MEP responses will be measured during rest and during an active contraction (Motor Tasks, see below) before and after BoMI training, as well as with and without SCS. To estimate changes in MEPs, response amplitudes under different conditions will be normalized to the baseline (before training, resting) response.

Motor tasks: Immediately before after the BoMI session, participants will wear a VR headset (Oculus Quest 2, Facebook, CA) to block their view. The IMUs on the legs will measure and digitize their leg joint angles. A real-time virtual representation of one of their joint angles will be presented through the VR. Participants will be asked to perform two tasks requiring different types of motor control. In the range-of-motion task, participants will be instructed to flex or extend their legs to surpass a virtual target of a specified amplitude. In the precision-control task, participants will have to move their joint and hold the position within a target range of a specified amplitude for 1 second. We will examine motor-evoked potentials elicited by TMS (*Aim 1*) and the StartReact response (*Aim 2*) as individuals perform the task under two conditions: with SCS and without SCS using the knee and ankle joints. As an alternative to the VR headset, a wall projector will be used to perform the motor tasks.

BoMI Training: Participants will perform visuo-spatial motor tasks over a 45min session with SCS. The tasks will consist of different types of game-like activities like center-out reaching, pong, solitaire, Tetris, and other flash games.

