Average MEP and StartReact responses (of 20 responses) will be used to quantify changes in corticospinal and reticulospinal tract excitability¹⁵. A paired sample t-test of response amplitude and latency (time from stimulation to muscle response) will be used to test the hypothesis that BoMI training with SCS results in enhanced corticospinal tract excitability during precision-control movements and reticulospinal tract excitability during range-of-motion movements. In addition, a Student's *t*-test with a Holm-Sidak adjustment for multiple comparisons will be performed to compare the difference between changes in corticospinal excitability induced by the type of motor task (precision control vs. range-of-motion), joint (ankle vs. hip), and group (control vs. SCI).

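### The secondary control-versus-SCI comparison is an unadjusted t-test between groups recruited from different sources, so a group difference could partly reflect age

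*Combined protocol and SAP*

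**What the plan says.** **Analysis.** Section 8 tests the main hypotheses with within-subject paired t-tests. It then adds a Student's t-test with Holm-Sidak adjustment on changes in corticospinal excitability, by type of motor task, "joint (ankle vs. hip), and group (control vs. SCI"). No covariate is named.

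**Use of controls.** Section 7.2 (Participants) uses controls to refine procedures, but adds: "Data collected on control subjects will also be used to establish baseline behavior for comparison of SCI participant task performance". About 16 unimpaired participants are expected for each type of protocol, against 12 SCI volunteers.

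**Recruitment.** Section 6.2 states: "Healthy subjects that are affiliated with Washington University will be recruited by flyers, and word of mouth". SCI volunteers are referred from neurosurgery, rehabilitation and community sites or identified through EPIC, and are also reached by fliers, phone and word of mouth. For two of the sites, "Recruitment from TRISL and Paraquad will be purely in the form of posting recruitment flyers and referrals".

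**Age.** Sections 5.1 and 5.2 set the same limit for both groups: "Age between 18 and 65 years". Nothing else in the plan concerns the age distribution. Section 5 aims for roughly equal numbers of men and women, without tying that to either group.

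**Normalisation.** Under Aim 1, for MEPs, "response amplitudes under different conditions will be normalized to the baseline (before training, resting) response". Aim 2 likewise normalises StartReact response times to baseline.

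**Expected composition.** Section 5 gives the St. Louis racial mix and says: "This will be the expected composition of our volunteer pool, of which the minority portion exceeds the national norm". Section 6.6 applies that mix to the SCI pool only, and says that recruitment of healthy minority subjects "typically matches the demographic composition of the Washington University community from which subjects will be recruited", with different percentages.

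**The concern.** A two-sample t-test between non-randomised groups estimates the effect of injury plus the effect of anything else that differs between them. Age is an obvious candidate: it plausibly affects reaction time, evoked-response latency and the response to training, and a common 18-65 limit leaves a 47-year span in which the two age distributions can differ. Holm-Sidak deals with multiplicity and does nothing about this.

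Baseline normalisation helps only in part. It removes a difference in starting level, but if older participants change less over a session, that remains in the normalised outcome. No normalisation is stated for MEP latency, which section 8 also analyses, or for the task-performance reference in section 7.2.

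Section 3.1 says the study will provide data for preparing a clinical trial. An age effect read as an injury effect would carry forward into that trial's design.

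**Working it through.** **1. Is age handled anywhere?** Eligibility (5.1, 5.2): 18-65 in both groups. Recruitment (6.2): different sources, no matching. Analysis (8): Student's t-test, no covariate. The answer is no.

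**2. How much could it matter?** The documents give neither an age difference nor an age-outcome correlation, so these inputs are assumptions shown as a range.

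- From the documents: 12 SCI; 16 controls per protocol type. If single-visit and five-visit controls are pooled at a visit, 16 + 16 = 32.
- Assumed: age gap 10 to 20 years; within-group age SD 12 years; correlation r of age with the outcome 0.1 to 0.4; no true injury effect.
- Spurious difference in outcome SDs: b = r × gap / 12.
- Noncentrality: δ = b / √(1/n₁ + 1/n₂). For 16 and 12, √(1/16 + 1/12) = 0.382.
- Error rate: probability that a noncentral t with 26 df and noncentrality δ exceeds the two-sided critical value.
- Strictest Holm-Sidak step, if there are three contrasts (task, joint, group): 1 − 0.95^(1/3) = 0.017.

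| Gap (years) | r | b (SD) | δ | Error at nominal 5% | Error at nominal 1.7% |
|---|---|---|---|---|---|
| 10 | 0.1 | 0.083 | 0.22 | 5.5% | 1.9% |
| 10 | 0.2 | 0.167 | 0.44 | 7.0% | 2.7% |
| 15 | 0.3 | 0.375 | 0.98 | 15.7% | 7.3% |
| 20 | 0.4 | 0.667 | 1.75 | 39.0% | 23.1% |

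With 32 controls the nominal-5% column becomes 5.7%, 7.7%, 19.1% and 48.6%. More controls make it worse, because the standard error shrinks and the bias does not.

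**3. What would adjustment cost in precision?** With 16 and 12, adding age multiplies the variance of the group estimate by about 1 + p × (gap/SD)², where p = 16 × 12 / 28² = 0.245. For a 10-year gap this is 1 + 0.245 × 0.694 = 1.17, so the standard error rises by about 8%. For 20 years it is 1 + 0.245 × 2.778 = 1.68, or about 30%. A smaller residual SD offsets part of this (factor √(1 − 0.4²) = 0.92 at r = 0.4).

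**4. Composition (editorial).** Section 5 states 44% Caucasian and 46% Black for the pool. Section 6.6 gives 78% white and 21% Black for healthy subjects, and 44% and 46% for SCI. Weighting by 100 and 12:

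- White: (100 × 0.78 + 12 × 0.44) / 112 = 83.28 / 112 = 74.4%.
- Black: (100 × 0.21 + 12 × 0.46) / 112 = 26.52 / 112 = 23.7%.

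Controls are 100/112 = 89% of the pool, so the two sections cannot both hold.

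**The case against.** **The age gap is assumed.** This stands. It is tempting to infer that university volunteers will be younger than people with chronic injury. The documents do not say so: section 6.2 assures recruits about benefits and employment status, which points to staff as well as students. Neither the direction nor the size of any imbalance can be shown.

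**The large error rates come from extreme inputs and are not those of the planned test.** This also stands. The 39% pairs the widest gap with the strongest correlation and ignores Holm-Sidak. At r = 0.1 and 10 years the error is close to nominal. The outcome is a normalised change, and the documents give no evidence of how strongly age relates to it.

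**The comparison is secondary.** Correct. The hypotheses under Aims 1 and 2 concern task and muscle and are tested within subjects, and group is one of three added contrasts. The section 7.2 use of controls as a performance reference has no stated test.

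**The groups have more in common than an age limit.** Correct. Both exclude pain conditions, major organ disease, recent analgesics, recent caffeine and epilepsy. SCI recruitment also uses flyers and word of mouth, and one referral source is the university's own neurosurgery department. None of this balances age.

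**Matching in age-by-sex cells would be awkward.** Accepted. Section 7.2 uses control sessions to refine procedures for SCI data collection, so many controls may be studied before the SCI age distribution is known. Three age bands by two sexes would leave about two SCI volunteers per cell (12/6). This argues for covariate adjustment, not for leaving the comparison unadjusted.

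**Conclusion.** The point holds for the secondary control-versus-SCI comparison only. As planned, that test cannot separate injury from age, and baseline normalisation protects only partly. For 12 against 16, the nominal 5% error would lie between about 5.5% and 39% before Holm-Sidak. At the strictest step of three contrasts it would be about 2% to 23% against a nominal 1.7%. These figures rest wholly on the assumed gap, SD and correlation; they show what the design leaves open and do not predict what will happen.

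A reader might infer that the study's main results are at risk. They are not: each person serves as their own control in the paired tests. A reader might also take the different racial compositions in section 6.6 as evidence of confounding. They show that the source populations differ, but they say nothing about age, and no planned analysis uses them. The mismatch with section 5 is clerical and adds no weight to the statistical point.

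**What to change.** In section 8, replace the unadjusted control-versus-SCI t-test with a linear model (ANCOVA) of the response change on group and age, and keep the Holm-Sidak adjustment across the contrasts. Report age and sex by group, including wherever controls serve as the reference for SCI task performance. Where practical, recruit the Visit 4 and Visit 5 controls across the whole 18-65 range, so that the adjustment does not extrapolate.

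The cost is small. Age is already needed to check eligibility at screening, and the model uses one degree of freedom. Precision falls if age and group are strongly associated (roughly 8% to 30% on the standard error for the assumed gaps, before any gain from a smaller residual). Spreading control recruitment may slow the filling of some age ranges. No matching and no additional participants are required.

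Separately, as an editorial correction, reconcile the expected composition in section 5 with section 6.6, either by limiting the St. Louis figures to the SCI group or by restating the figures for the whole pool.

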6.3 Potential benefits of the proposed research to the subjects and others

There is no expected direct benefit to study subjects. If this study is able to identify specific neural tracts that are involved in movements enhanced by spinal cord stimulation, we may implement this knowledge for the development of patient-specific rehabilitation strategies towards improvement of movement after SCI. Society may benefit from a novel paradigm for restoration of function after SCI.

6.4 Compensation

There will be no costs to participants for being in this study. Participants with SCI will be paid \$20 for every hour of participation during this research study. Unimpaired participants will be paid \$10 for every hour of participation. A prorated rate of \$5 dollars for every completed 15 and 30 minutes for SCI and Control participants respectively will be used to account for incomplete hours or participation. If they withdraw from the study, they will be paid for a percentage of the experiment that they participated. The maximum amount of money that they can receive for a visit to the lab is \$60. Transportation expenses from home to the hospital will be reimbursed when needed. Transportation expenses from home to the hospital will be reimbursed upon receipt. These funds are provided to help support participants with time and travel associated with participation.

6.5 Inclusion of women

Studies actively encourage the participation of women in the research. Our studies routinely and deliberately attempt to include equivalent numbers of women and men. However, due to a small size of the study, we may not be able to enroll equal number of male and female subjects. Pregnant or possibly pregnant women are excluded from our research protocols.

6.6 Inclusion of minorities

All of our studies actively encourage the participation of minorities in the research. Our minority recruiting of healthy subjects typically matches the demographic composition of the Washington University community from which subjects will be recruited (78% white, 21% Black, <1 % Hispanic). The racial composition of the population in St. Louis is approximately 44% Caucasian, 46% Black or African American, 4% Asian, 4% Hispanic, 2% Other. This will be the expected composition of our SCI volunteer pool, of which the minority portion exceeds the national norm.

6.7 Inclusion of children

Due to the newly identified rare risk of autonomic dysreflexia, children will not be included in the study.

7. Study design and methods

